6.5 Management of Infusion Reactions

Infusion-related reactions may occur during the infusion of study treatment. The infusion should be administered at a site properly equipped and staffed to manage anaphylaxis should it occur. All supportive measures consistent with optimal patient care should be given throughout the study according to institutional standards. Supportive measures may include extending the infusion time and/or administering medications for infusion-related reactions.

Patients who have experienced an infusion-related reaction should be pre-medicated for subsequent infusions. Premedication may include acetaminophen, an antihistamine, and a corticosteroid administered 30–60 minutes prior to each infusion or according to institutional standards.

If anaphylaxis occurs, study treatment administration should be immediately and permanently discontinued.

6.6 Management of Suspected PML

Signs and symptoms of progressive multifocal leukoencephalopathy (PML) may include altered mental status, motor deficits such as hemiparesis or ataxia, visual disturbances, or higher cortical dysfunction such as dysphasia or agnosia. See the Investigator's Brochure for further details.

If PML is suspected, hold further dosing and undertake a diagnostic work-up including (but not limited to):

- Neurologic examinations, as warranted
- Brain radiologic features by magnetic resonance imaging (MRI)
- PCR analysis: John Cunningham virus (JCV) DNA detectable in cerebrospinal fluid

If PML is confirmed, Brentuximab Vedotin should be permanently discontinued.

6.7 Expected Duration of Subject Participation

6.7.1 Duration of Therapy

The treatment will be continued until disease progression, unacceptable toxicity, stem cell transplantation, or at physician discretion. If a patient has completed 17 cycles, the treating physician can determine if to continue or discontinue treatment in event there is no disease progression or unacceptable toxicity.

6.7.2 Duration of Follow Up

After completion of the study the subjects will be followed for a total of 3 years. The follow up visits will be done at 6, 12, 24 and 36 months after the last cycle of therapy. If the patient is unable to follow up with the local site in person, virtual visits may be used to capture applicable procedures during long-term follow up only.

The follow up visits should include the following:

- Physical Examination
- Vital signs
- Height and weight
- CBC with differential
- Serum chemistry panel as outlined in section **11.1.2**
- ECOG performance status
- Adverse event evaluation (only the adverse events attributed to the study drug)
- Diagnostic CT neck, chest, abdomen and pelvis scan with IV and PO contrast will be done at 6, 12 and 24 months if no disease progression. Neck CT can be omitted if no involvement at baseline

If a virtual visit is completed in follow up every attempt should be made to complete the required assessments listed above, though if they are not completed it will not be considered a protocol deviation.

Patients who have progressive disease or start a new treatment are not required to come in for clinical follow up. These patients can be contacted over the phone by the study personnel to obtain the following information

- Disease status
- Adverse event evaluation only if patients have residual persistent symptoms related to BV treatment
- Current lymphoma treatment

Patients will be followed for toxicity for 30 days after treatment has been discontinued or until death, whichever occurs first. The clinical course of each event will be followed until resolution, stabilization, or until has been determined that the study treatment or participation is not the cause.

Serious adverse events (SAE) that are still ongoing at the end of the study period will necessitate follow-up to determine the final outcome. Any serious adverse event that occurs after the study period and is considered to be possibly related to the study treatment or study participation will be recorded and reported immediately.

7.0 RECOMMENDED DOSE MODIFICATIONS

Table 2 describes the recommended dose modifications for study treatment-associated neuropathy.

Doses reduced for treatment-related neuropathy should not be re-escalated without discussion with the primary site, CCF study team.

Table 2

| Grade of Neuropathy | Recommended Dose Modification | |
|---------------------|-------------------------------|--------------------------|
| | Sensory Neuropathy | Motor Neuropathy |
| 1 | Continue at same dose | Continue at same dose |
| 2 | Continue at same dose | Reduce dose to 1.2 mg/kg |
| 3 | Reduce dose to 1.2 mg/kg | Discontinue treatment |
| 4 | Discontinue treatment | Discontinue treatment |

Brentuximab Vedotin should be held for grade >2 hematological (anemia, neutropenia, and thrombocytopenia only) and non-hematological (except neuropathy) toxicities that are deemed possibly related to BV. Patients with bone marrow involvement at baseline may continue study treatment through cycle 4 despite having grade 3-4 neutropenia or thrombocytopenia. If those counts have not recovered to grade ≤ 2 prior to beginning cycle 5 and are considered at least possibly related to BV, then you must get approval from the sponsor-investigator ([name]) prior to starting cycle 5.

For grade >2 hematological toxicity, the study drug can be restarted at the same dose once the toxicity has resolved to grade ≤ 2 or has returned to baseline. If study drug was held for neutropenia, growth factor support to be considered for the treatment or prophylaxis with subsequent cycles. Consider discontinuing or dose reducing Brentuximab Vedotin to 1.2 mg/kg in patients with recurring grade 4 neutropenia even with use of growth factors. In patients with grade 3 non-hematological toxicity the study drug can be restarted at the same dose once the toxicity has resolved to grade ≤ 2 or

CASE 1415

Protocol Version Date: 07/06/2021

has returned to baseline. In patients with grade 4 non-hematological toxicity the study drug can be restarted once the toxicity has resolved to grade ≤2 or has returned to baseline at a reduced dose of 1.2 mg/kg. The study drug can be discontinued at investigator's discretion in patients who developed grade 4 non-hematological toxicity. No further dose reductions of Brentuximab Vedotin other than mentioned above are permitted. If further reduction is required, the study drug should be discontinued. The study drug can be held for 3 weeks for toxicity. Delays >3 weeks are not permitted without approval from the primary study team at CCF.

8.0 ADVERSE EVENTS: LIST AND REPORTING REQUIREMENTS

The following is a list of AEs (Section 8.2) and the reporting requirements associated with observed AEs and SAEs (Sections 8.3 and 8.4).

The clinical course of each event will be followed until resolution, stabilization, or until it has been determined that the study treatment or participation is not the cause.

Serious adverse events that are still ongoing at the end of the study period will necessitate follow-up to determine the final outcome. Any serious adverse event that occurs after the study period and is considered to be possibly related to the study treatment or study participation will be recorded and reported immediately.

8.1 Adverse Events and Potential Risks

8.1.1 Brentuximab Vedotin

Brentuximab Vedotin (SGN-35) is an antibody drug conjugate (ADC) consisting of the chimeric anti-CD30 monoclonal antibody, SGN-30, chemically conjugated to the anti-microtubule agent monomethyl auristatin E (MMAE)

Detailed information describing the side effects, preparation, administration, packaging and storage of Brentuximab Vedotin is located in the Pharmaceutical Information (section 9).

8.2 Definitions

8.2.1 Adverse Events

An **adverse event** (AE) is any unfavorable or unintended event, physical or psychological, associated with a research study, which causes harm or injury to a research participant as a result of the participant's involvement in a research study. The event can include abnormal laboratory findings, symptoms, or disease associated with the research study. The event does not necessarily have to have a causal relationship with the research, any risk associated with the research, the research intervention, or the research assessments.

- **External adverse events** are adverse events experienced by subjects enrolled in multicenter clinical trials at sites other than the site(s) over which the Institutional Review Board has jurisdiction.

- **Internal adverse events** are adverse events experienced by subjects enrolled at the site(s) under the IRB's jurisdiction for either multicenter or single-center research projects.

8.2.2 Serious Adverse Events

A **serious adverse event** (SAE) is any adverse experience occurring at any dose that results in any of the following outcomes:

- Results in **death**.
- Is **life-threatening** adverse experience. The term life threatening in the definition of serious refers to an adverse event in which the subject was at risk of death at the time of the event. It does not refer to an adverse event, which hypothetically might have caused death if it were more severe.
- Requires inpatient hospitalization or prolongation of existing hospitalization. Any adverse event leading to hospitalization or prolongation of hospitalization will be considered as Serious, UNLESS at least one of the following expectations is met:
 - The admission results in a hospital stay of less than 12 hours OR
 - The admission is pre-planned (i.e., elective or scheduled surgery arranged prior to the start of the study) OR
 - The admission is not associated with an adverse event (e.g., social hospitalization for purposes of respite care).

However, it should be noted that invasive treatment during any hospitalization may fulfill the criteria of "medically important" and as such may be reportable as a serious adverse event dependent on clinical judgment. In addition, where local regulatory authorities specifically require a more stringent definition, the local regulation takes precedent.

- Results in **persistent or significant disability/incapacity**. The definition of disability is a substantial disruption of a person's ability to conduct normal life's functions.
- Is a **congenital anomaly/birth defect**.
- Is an **important medical event**. Important medical events that may not result in death, be life-threatening, or require hospitalization may be considered a serious adverse experience when, based upon appropriate medical judgment, they may jeopardize the patient or subject and may require medical or surgical intervention to prevent one of the outcomes listed in this definition. Examples of such medical events include allergic bronchospasm requiring intensive treatment in an emergency room or at home, blood disease or disorders, or convulsions that do not result in inpatient hospitalization, or the development of drug dependency or drug abuse.

8.2.3 Adverse Event / Serious Adverse Event Data Collection

All AEs (regardless of relationship to study drug) will be captured from the time the subject signs the ICF through the end of the safety-reporting period.

All active symptoms and current / historical medical conditions present at the time of the baseline assessment will be collected; these will be considered baseline

symptoms / prior medical history.

Any medical condition that was present at the baseline visit (prior to study treatment) and that remains unchanged, or improved, should not be recorded as an AE. If there is a worsening of a medical condition that was present at the baseline visit, then this should be considered a new AE and recorded appropriately.

If a sign or symptom is one component of a diagnosis or syndrome, then only the diagnosis or syndrome should be recorded on the AE page of the CRF.

The following information should be considered when determining whether or not to record a test result, medical condition, or other incident on the Adverse Events and Pre-existing Conditions case report form (CRF):

- Complications that occur in association with any procedure (e.g., biopsy) should be recorded as AEs whether or not the procedure was protocol mandated. Changes in medical conditions and adverse events, including changes in severity, frequency, or character, during the safety-reporting period should be recorded.
- In general, an abnormal laboratory value should not be recorded as an adverse event unless it is associated with clinical signs or symptoms, requires an intervention, results in a serious adverse event, or results in study termination or interruption/discontinuation of study treatment. When recording an adverse event resulting from a laboratory abnormality, the resulting medical condition rather than the abnormality itself should be recorded (e.g., record "anemia" rather than "low hemoglobin").

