8.2.4 Adverse Event / Serious Adverse Event Evaluation and Documentation

The investigator or designee is responsible for ensuring that all adverse events (both serious and non-serious) observed by the clinical team or reported by the subject are fully recorded in the subject's medical records. Source documentation must be available to support all adverse events.

The investigator or sub-investigator will provide the following for all adverse events (both serious and non-serious):

- Event term (as per CTCAE)
- Description of the event
- Date of onset and resolution
- Expectedness of the toxicity
- Grade of toxicity
- Attribution of relatedness to the investigational agent- (this must be assigned by an investigator, sub-investigator, or treating physician)
- Action taken as a result of the event, including but not limited to; no changes, dose interrupted, reduced, discontinued, etc. or action taken with regard to the event, i.e. no action, received conmed or other intervention, etc.
- Outcome of event

All participating investigators will assess the occurrence of AEs from the time the subject signs the ICF through the end of the safety-reporting period. Subjects will be

CASE 1415

Protocol Version Date: 07/06/2021

followed for toxicity for 30 days after treatment has been discontinued or until death, whichever occurs first (safety-reporting period). The clinical course of each event will be followed until resolution, stabilization, or until it has been determined that the study treatment or participation is not the cause.

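### Symptom-free grade 3-4 neutropenia or thrombocytopenia in marrow-involved patients may not be captured as an AE, because section 7 removes the hold that would trigger recording under section 8.2.3

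*Combined protocol and SAP*

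**What the plan says.** Section 8.2.3 gives a default for laboratory values: "In general, an abnormal laboratory value should not be recorded as an adverse event unless it is associated with clinical signs or symptoms". The sentence then adds the other routes by which a value becomes an AE, namely that it "requires an intervention, results in a serious adverse event, or results in study termination or interruption/discontinuation of study treatment". Severity grade is not among them. Section 8.2.4 requires grade and "Attribution of relatedness to the investigational agent" for each AE.

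Section 7.0 sets the default action on blood counts: "Brentuximab Vedotin should be held for grade >2 hematological (anemia, neutropenia, and thrombocytopenia only"), where the toxicity is deemed possibly related to the drug. It then makes an exception: "Patients with bone marrow involvement at baseline may continue study treatment through cycle 4 despite having grade 3-4 neutropenia or thrombocytopenia". The exception ends with a condition on counts not recovered to grade 2 or below "prior to beginning cycle 5 and are considered at least possibly related to BV"; in that case the sponsor-investigator must approve the start of cycle 5.

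Section 4.1.5 waives the ANC and platelet entry limits for patients with documented marrow involvement, so these patients may start with low counts. Section 8.2.3 also has a rule for baseline conditions: "If there is a worsening of a medical condition that was present at the baseline visit, then this should be considered a new AE".

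**The concern.** Each section is workable alone. Read together, they make the recording of a severe blood count depend on what is done about it. In most patients a possibly related grade 3-4 neutropenia or thrombocytopenia leads to a hold, and the hold is an interruption, which is a recording trigger. Section 7 removes that step for marrow-involved patients through cycle 4, and 8.2.3 puts nothing in its place.

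What is at stake is the haematological AE rate. It could be too low, and low to a different degree by marrow status, in a single-arm trial that has no control rate to offset under-capture. The patients affected are also those who may enter without meeting the usual count limits. The primary endpoint, ORR, is not affected.

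**Working it through.** The plan states no figure on this point, so there is none to reproduce. The check is a reading of sections 7.0 and 8.2.3 side by side, followed by simple arithmetic on the possible size.

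**Step 1: apply both rules to the same new, asymptomatic, untreated, non-serious grade 4 neutropenia.**

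| Situation | Hold under 7.0? | Trigger under 8.2.3 | Entered as an AE? |
|---|---|---|---|
| No marrow involvement, possibly related | Yes | Interruption | Yes |
| Marrow involvement, cycles 1-4, possibly related | Not required | None | Need not be |
| Any patient, judged unlikely related or unrelated | Not required | None | Need not be |

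The first two rows differ only in marrow status. The third row rests on reading the relatedness condition in 7.0 as applying to haematological as well as non-haematological toxicity, which is the natural reading of the sentence. It sits awkwardly with 8.2.3, which says AEs are captured whatever their relationship to the drug.

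**Step 2: mark what falls outside the gap.**

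- If the patient has symptoms, receives a transfusion or growth factor (both permitted by section 6.4), or has an SAE, a trigger is met and the event is recorded.
- Section 7.0 exempts neutropenia and thrombocytopenia, not anaemia. Anaemia is affected only through the third row.
- A baseline cytopenia that does not change is not an AE under 8.2.3, and rightly so.
- A baseline cytopenia that worsens is unclear. The worsening rule points to a new AE, but it speaks of a medical condition and does not say that it overrides the laboratory rule.

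**Step 3: look for text that closes the gap.** No passage makes a grade 3-4 count an AE regardless of the triggers. Section 14.0 plans no summary of laboratory values by grade and no shift table. A CBC is drawn on day 1 of every cycle (section 11.1.5), so the counts exist, but grade and attribution are required only for AEs.

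**Step 4: size.** The planned enrolment is 31 (section 15.0). The documents do not give the marrow-involved share, so I assume a range:

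- 10%: 0.10 × 31 = 3.1 patients
- 40%: 0.40 × 31 = 12.4 patients

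One patient missed among 31 is 1/31 = 3.2 percentage points. For scale, section 9.3 lists neutropenia at 21% and thrombocytopenia at 10%:

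- In all 31 patients: 0.21 × 31 = 6.5 and 0.10 × 31 = 3.1 cases.
- In 3.1 to 12.4 marrow-involved patients: neutropenia 0.21 × 3.1 = 0.7 to 0.21 × 12.4 = 2.6; thrombocytopenia 0.10 × 3.1 = 0.3 to 0.10 × 12.4 = 1.2.

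Section 9.3 does not say that these rates are grade 3-4. Some cases would also be symptomatic or treated and so recorded anyway. At these rates the second set of figures is therefore a ceiling. Marrow-involved patients could have higher rates than those listed, and the documents do not settle that.

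**The case against.** The strongest reply is that 8.2.3 is guidance. It opens with a qualifier, and it stands in a list of points to weigh when deciding whether to record. Section 8.2.1 allows abnormal laboratory findings to be AEs. Section 8.2.5 gives an asymptomatic laboratory finding as an example of a grade 1 event. The AE fields in 8.2.4 allow for no action taken. A careful investigator could record every one of these counts. That is true, and it means the gap is a risk and not a certainty. It does not close the gap: the specific rule on laboratory values points towards not recording, and sites left to their own judgement may apply it differently.

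The second reply is that different handling by marrow status is partly correct, since these patients may enter with low counts and an unchanged baseline count is not a toxicity. This stands, and it limits the point to new or worsened values.

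The third reply is that section 14.0 specifies no haematological AE rate, so no planned estimate or decision changes. This also stands as far as it goes. Section 8 nevertheless requires AEs to be collected and graded, and any rate later reported from those data would carry the problem.

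**Conclusion.** The point holds in a limited form. New or worsened grade 3-4 neutropenia or thrombocytopenia that is asymptomatic, untreated and non-serious may not be captured as a graded, attributed AE in marrow-involved patients through cycle 4, nor in any patient whose cytopenia is judged not possibly related. Haematological AE rates may be under-counted, and counted differently by marrow status. The size is unknown; about 3-12 patients would be under the exemption if 10-40% of 31 have marrow involvement, which is an assumption. The fix is worth making because a stated rule, and not a missing detail, produces the difference.

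A reader might infer four stronger things that the documents do not support:

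- That severe haematological toxicity goes unrecorded altogether. The counts are taken each cycle, and only the AE entry may be missing.
- That the cycle 5 approval has no attribution to act on. Section 7.0 itself asks whether the counts "are considered at least possibly related to BV", and nothing says that this judgement goes undocumented.
- That 84 days of toxicity (4 cycles × 21 days) could be missed per patient. That is the length of the window. The cycle 1 day 1 count is taken before any drug, so the exemption can act on new toxicity only from the cycle 2 dose.
- That liver tests need the same exception. Section 7.0 exempts no liver test, so they are not captured differently by marrow status. Including them would revise the general AE convention beyond what this point shows.

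**What to change.** Add one sentence to section 8.2.3, after the rule on laboratory values:

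> Exception: any new grade 3 or higher neutropenia, thrombocytopenia or anemia, or worsening from baseline to a higher grade of 3 or above, is recorded as an AE with CTCAE grade and attribution, whether or not it causes symptoms, intervention or interruption of treatment; an unchanged baseline cytopenia is not a new AE.

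Anaemia is included because the relatedness route applies to it, although the marrow exemption does not. The dosing rules in section 7.0 stay as they are; this changes recording only.

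The cost is one sentence and some additional AE entries, based on blood already drawn each cycle. Some of those entries will reflect lymphoma and not the drug, which the attribution field can show.

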8.2.4 Adverse Event / Serious Adverse Event Evaluation and Documentation

The investigator or designee is responsible for ensuring that all adverse events (both serious and non-serious) observed by the clinical team or reported by the subject are fully recorded in the subject's medical records. Source documentation must be available to support all adverse events.

The investigator or sub-investigator will provide the following for all adverse events (both serious and non-serious):

- Event term (as per CTCAE)
- Description of the event
- Date of onset and resolution
- Expectedness of the toxicity
- Grade of toxicity
- Attribution of relatedness to the investigational agent- (this must be assigned by an investigator, sub-investigator, or treating physician)
- Action taken as a result of the event, including but not limited to; no changes, dose interrupted, reduced, discontinued, etc. or action taken with regard to the event, i.e. no action, received conmed or other intervention, etc.
- Outcome of event

All participating investigators will assess the occurrence of AEs from the time the subject signs the ICF through the end of the safety-reporting period. Subjects will be

CASE 1415

Protocol Version Date: 07/06/2021

followed for toxicity for 30 days after treatment has been discontinued or until death, whichever occurs first (safety-reporting period). The clinical course of each event will be followed until resolution, stabilization, or until it has been determined that the study treatment or participation is not the cause.

